## 8.5 Treatment of Overdose

For purposes of this study, an overdose will be defined as any dose of any drug administered as part of the study exceeding the dose prescribed by the protocol. It is up to the investigator or the reporting physician to decide whether a dose is to be considered an overdose, in consultation with the Sponsor.

#### 8.6 Pharmacokinetics

Plasma samples for evaluation of MK-6482 and PT3317 PK will be collected at scheduled time points as delineated in the SoA.

The decision as to which plasma samples collected will be measured for evaluation of PK will be collaboratively determined by the Sponsor. If indicated, these samples may also be measured and/or pooled for assay in an exploratory manner for metabolites.

## 8.6.1 Blood Collection for Plasma MK-6482 and PT3317

Sample collection, storage, and shipment instructions for plasma samples will be provided in the Study Operations Manual.

#### 8.7 Pharmacodynamics

Blood samples for erythropoietin analysis will be collected at scheduled time points as delineated in the SoA.

#### 8.8 Biomarkers

Collection of samples for other biomarker research is also part of this study. The following samples for biomarker research are required and will be collected from all participants as specified in the SoA:

• Blood for genetic analysis

#### 8.8.1 Planned Genetic Analysis Sample Collection

The planned genetic analysis sample will be drawn for UGT2B17 and CYP2C19 genotyping and for planned analysis of the association between genetic variants in DNA and drug response. If the IRB/IEC does not approve of the planned analysis of the association between DNA variation and drug response, or if there is a local law or regulation prohibiting the same, data analysis will be limited to UGT2B17 and CYP2C19. Leftover extracted DNA will be stored for FBR if the participant provides documented informed consent for FBR.

Sample collection, storage, and shipment instructions for planned genetic analysis samples will be in the operations/laboratory manual.

#### 8.9 Future Biomedical Research Sample Collection

If the participant provides documented informed consent for FBR, the following specimens will be obtained as part of FBR:

• Leftover DNA for future research

## 8.10 Health Economics Medical Resource Utilization and Health Economics

Not applicable

MK-6482-020-02 FINAL PROTOCOL

69

#### 8.11 Visit Requirements

Visit requirements are outlined in Section 1.3. Specific procedure-related details are provided in sections below.

#### 8.11.1 Screening

Approximately 28 days before administration of study intervention, potential participants will be evaluated to determine that they fulfill the entry requirements as set forth in Section 5.

Participants may be rescreened after consultation with the Sponsor. Rescreening should include all screening procedures listed in the SoA, including consent review. Rescreen procedures cannot be conducted the day prior to intervention allocation/randomization if there are Day -1 procedures planned per protocol.

#### 8.11.2 Treatment Period

Refer to the SoA (Section 1.3).

## 8.11.3 Discontinued Participants Continuing to be Monitored in the Study

At any point if a participant discontinues from the study but continues to be monitored in the study, all study procedures specified in the SoA may be completed at the discretion of the investigator and with Sponsor agreement.

## 8.11.4 Poststudy (Follow-up)

All participants who received the study intervention (including participants who terminate the study early) will return to the CRU approximately 14 days after study intervention administration for poststudy (follow-up) procedures, and to determine if any AE has occurred since the last study visit. If the poststudy visit occurs less than 14 days after administration of study intervention, a subsequent follow-up telephone call should be made at 14 days post administration of study intervention to determine if any AEs have occurred since the poststudy clinic visit.

#### 8.11.5 Critical Procedures Based on Study Objectives: Timing of Procedure

For this study, the blood sample for MK-6482 and PT3317 is the critical procedure.

At any postdose time point, the blood sample for MK-6482 and PT3317 need to be collected as close to the exact time point as possible. All other procedures should be completed as close to the prescribed/scheduled time as possible. Study procedures can be performed before or after the prescribed/scheduled time.

The order of priority can be changed during the study with joint agreement of the investigator and the Sponsor Clinical Director.

Any nonscheduled procedures required for urgent evaluation of safety concerns take precedence over all routine scheduled procedures.

The following variance in procedure collection times will be permitted.

• PK Collection as outlined in Table 6.

 Table 6
 Postdose Pharmacokinetic (Blood) Collection Windows

| PK Collection        | PK Collection Window                        |
|----------------------|---|
| (relative to dosing) | (relative to scheduled time for collection) |
| 0 to 2 hours         | 5 min                                       |
| >2 to 12 hours       | 15 min                                      |
| >12 to 48 hours      | 1 hour                                      |
| >48 to 120 hours     | 2 hours                                     |

- Postdose standard safety evaluations: vital signs, ECG, pulse oximetry, and laboratory safety tests
  - Prior to 24-hours postdose may be obtained within 15 minutes of the theoretical sampling time
  - Between 24-hours and 48-hours postdose may be obtained within 1 hour of the theoretical sampling time
  - From 48-hours to 120-hours postdose may be obtained within 2 hours of the theoretical sampling time.

# 8.11.6 Study Design/Dosing/Procedures Modifications Permitted Within Protocol Parameters

This is a Phase 1 assessment of MK-6482 in humans, and the PK, pharmacodynamic, and safety profiles of the compound are still being elucidated. This protocol is written with some flexibility to accommodate the inherent dynamic nature of Phase 1 clinical studies. Modifications to clinical or laboratory procedures currently outlined may be required to achieve the scientific goals of the study objectives and/or to ensure appropriate safety monitoring of the study participants.

- Instructions to take study intervention with or without food or drink may also be modified based on newly available data
- Modification of the PK/pharmacodynamic sample processing and shipping details based on newly available data

The PK sampling scheme currently outlined in the protocol may be modified during the study based on newly available PK data (eg, to obtain data closer to the time of peak plasma concentrations). If indicated, these collected samples may also be assayed in an exploratory manner for metabolites and/or pharmacodynamic markers.

Up to additional 50 mL of blood may be drawn for safety and/or PK analyses. The total blood volume withdrawn from any single participant will not exceed the maximum allowable volume during their participation in the entire study (Appendix 8).

The timing of procedures for assessment of safety procedures (eg, vital signs, ECG, safety laboratory tests, pulse oximetry, etc) may be modified during the study based on newly available data. Additional safety laboratory tests may be added to blood samples previously drawn to obtain additional safety information. These changes will not increase the number of study procedures for a given participant during their participation in the entire study.

It is understood that the current study may use some or none of the alterations described above. Any alteration made to this protocol to meet the study objectives must be detailed by the Sponsor in a letter to the Study File and forwarded to the investigator for retention. The letter may be forwarded to the IRB/IEC at the discretion of the investigator.

# 9 STATISTICAL ANALYSIS PLAN

Data will be handled and process according to Celerion SOPs, which are written based on the principles of GCP.

## 9.1 Statistical Analysis Plan Summary

This section contains a brief summary of the statistical analyses for this study. Full detail is in the SAP to be provided separately.

Detailed methodology for summary and statistical analyses of the data collected in this study will be documented in an SAP. The SAP will be prepared by Celerion and agreed upon with the Sponsor. This document may modify the plans outlined in the protocol; however, any major modifications of the primary endpoints definition and/or its analysis will also be reflected in a protocol amendment. Additional statistical analyses other than those described in this section may be performed if deemed appropriate.

# 9.2 Responsibility for Analyses

The statistical analysis of the data obtained from this study will be conducted by the Data Management and Biometrics department at Celerion.

If, after the study has begun, changes are made to the statistical analysis stated below, then these deviations to the plan will be listed, along with an explanation as to why they occurred, in the CSR.

# 9.3 Hypotheses/Estimation

Primary Estimation:

Estimation 1: The plasma PK (AUC0-inf and Cmax) of MK-6482 following a single oral 80 mg dose of MK-6482 to participants with moderate hepatic impairment will be estimated and compared to those in healthy matched control participants.

## 9.4 Analysis Endpoints

The primary PK endpoints will be AUC0-inf and Cmax of MK-6482 following a single oral dose of MK-6482 to participants with moderate hepatic impairment compared to those in healthy matched control participants.

Additional PK endpoints will be other PK parameters of MK-6482 including AUC0-last, AUC0-24, AUC%extrap, C24, Tmax, apparent terminal t/2,  $\lambda z$ , CL/F and Vz/F. Relevant PK parameters for PT3317 will also be presented.

## 9.5 Analysis Populations

The following populations are defined for the analysis and reporting of data. All participants will be reported, and their data analyzed, according to the study intervention(s) they actually received.

*All Participants as Treated (APaT):* The All Participants as Treated Population consists of all participants who received the study intervention. This population will be used for assessments of safety and tolerability.

*Per-Protocol (PP)*: The Per-Protocol Population consists of the subset of participants who comply with the protocol sufficiently to ensure that generated data will be likely to exhibit the effects of treatment, according to the underlying scientific model. Compliance covers such considerations as exposure to treatment, availability of measurements and absence of important protocol deviations. Important protocol deviations will be identified to the extent possible prior to unblinding by individuals responsible for data collection/compliance, and its analysis and interpretation. Any participants or data values excluded from analysis will be identified, along with their reason for exclusion, in the CSR. At the end of the study, all participants who are compliant with the study procedure as aforementioned and have available data considered sufficient to exhibit the effect of treatment will be included in the Per-Protocol dataset. This population will be used for the PK analyses.

## 9.6 Statistical Methods

## 9.6.1 **PK Descriptive Statistics**

Individual values will be listed for each PK parameter by group and analyte, and the following (non-model-based) descriptive statistics will be provided: N (number of participants with non-missing data), arithmetic mean, standard deviation, arithmetic percent

MK-6482-020-02 FINAL PROTOCOL

CV (calculated as 100 x standard deviation/arithmetic mean), median, minimum, maximum, geometric mean, and geometric percent CV (calculated as 100 x sqrt( $\exp(s^2) - 1$ ), where s is the observed variance on the natural log-scale.

# 9.6.2 PK Statistical Analysis

Separately for each PK parameter, individual values of MK-6482 AUC0-inf, AUC0-24, and Cmax will be natural log-transformed and evaluated with a linear mixed effects model containing a fixed effect for population (hepatic impairment group and normal hepatic function group). An unstructured covariance matrix will be used to allow for unequal population variances via the REPEATED and GROUP statement in SAS PROC MIXED. Kenward and Roger's method will be used to calculate the denominator degrees of freedom for the fixed effect (DDFM=KR). Ninety percent (90%) CIs for the least squares means for each population will be constructed on the natural log scale and will reference the t-distribution. Exponentiating the least-squares means and their corresponding 90% CIs will yield estimates for the population geometric means and confidence intervals about the geometric means on the original scale. Sample SAS code is given below:

proc mixed data=data; class population; model lnpk = population /ddfm=kr; repeated/ group= population type=UN; lsmeans population /cl alpha=0.1; run;

To compare participants with hepatic impairment to participants with normal hepatic function, a two sided 90% CI for the difference in least-squares means (hepatic impairment – normal hepatic function) will be calculated for each PK parameter using the aforementioned model. These confidence limits will be exponentiated to obtain the 90% confidence interval for the ratio of geometric means (hepatic impairment/normal hepatic function) for each PK parameter. A sensitivity analysis may be performed without poor metabolizers at UGT2B17 or CYP2C19 if applicable as deemed clinically appropriate.

Figures showing summary concentration-time profiles by hepatic impairment category for both MK-6482 and PT3317 (linear plot with arithmetic mean (±SD) for concentration and semi-log plot with arithmetic mean) will be provided. Individual participant concentrationtime profiles may also be provided in the appendix separately and/or as overlays using hepatic impairment category as grouping variable. A table showing summary PK parameter values with GMs (%GCV) by population, will be provided for PK parameters, AUC0-inf, AUC0-last, AUC0-24, Cmax, C24, Tmax, apparent terminal t½, CL/F (parent only), and Vz/F (parent only). A table showing the GMR (hepatic impairment/normal hepatic function) and corresponding 90% CI will be provided for PK parameters, AUC0-inf, AUC0-24, and Cmax.

Individual values will be listed for each PK parameter for MK-6482 (AUC0-inf, AUC0-last, AUC0-24, Cmax, C24, Tmax, apparent terminal  $t_{2}^{1/2}$ , CL/F, Vz/F, AUC%extrap[percentage of AUC0-inf obtained by extrapolation],  $\lambda z$  [terminal elimination rate constant]) and PT3317 (AUC0-inf, AUC0-last, AUC0-24, Cmax, C24, Tmax, apparent terminal  $t_{2}^{1/2}$ , MPR for Cmax [metabolite to parent ratio for Cmax] and MPR for AUC0-inf [metabolite to parent ratio for AUC0-inf]) by group, and the following (non-model-based) descriptive statistics will be provided: N (number of participants with non-missing data), arithmetic mean, standard deviation, arithmetic percent CV (calculated as 100 x standard deviation/arithmetic mean), median, minimum, maximum, geometric mean, and geometric percent CV (calculated as 100 x sqrt(exp(s) - 1), where s is the observed variance on the natural log-scale). PK concentration listings for MK-6482 in plasma and PT3317 will also be provided for each participant. Descriptive statistics may be provided based on UGT2B17 and/or CYP2C19 phenotypes separately.

The relationship between MK-6482 PK and hepatic impairment will be examined in an exploratory manner via a scatter plot of PK values (AUC0-inf, AUC0-24, Cmax, Tmax, and apparent terminal t/2) versus the Child-Pugh score. Plots of PK values (AUC0-inf, AUC0-24, Cmax, Tmax, and apparent terminal t/2) and the baseline laboratory components of the Child-Pugh score (ie, bilirubin, albumin levels, and prothrombin time) will be provided. Plots of PK parameter values (AUC0-inf, AUC0-24, Cmax, Tmax, and apparent t/2) versus age and BMI will also be provided.

Descriptive statistics for aforementioned PK parameters will also be provided by NCI classification.

# 9.6.3 Safety Analysis

For safety, all AEs, vital signs, ECGs, pulse oximetry, and safety laboratory values will be listed for each participant and tabulated by group. Summary statistics for the safety laboratory tests, vital signs, and/or ECGs may also be computed and provided, as deemed clinically appropriate.

# 9.7 Pharmacodynamics Analysis

Summary statistics by time point and plots may be generated for erythropoietin as well as for change from baseline, as deemed clinically appropriate.

## 9.8 Interim Analyses

Not applicable

# 9.9 Multiplicity

Not applicable

#### 9.10 Sample Size and Power Calculations

The sample size selected for each population to evaluate the effect of hepatic impairment on the PK of MK-6482 was not chosen to satisfy any a priori statistical requirement. This sample size (N=8 per group) has historically been shown to be sufficient for studies of this type and should provide adequate data to support the planned analyses. Nevertheless, estimates of the expected precision of the estimates, based on these sample sizes and the known variability obtained from hepatic PK studies are presented below.

The precision of the estimated GMRs (hepatic impairment / normal hepatic function) of PK parameters obtained from this study can be assessed by calculating the half-width of the 90% CIs expected for the given sample size and assumed variability. The observed between-participant coefficients of variation were 62.44% (~0.574 standard deviation on the log scale) and 56.29% (~0.525 standard deviation on the log scale) for AUC0-inf from food-effect study (Protocol MK-6482-002) and comparative bioavailability study (Protocol MK-6482-006), respectively. Assuming a sample size of 8 participants per population and observed between-participant SD is 0.574 on the log scale, then the half width of the 90% CI of GMR for MK-6482 AUC0-inf on the log scale will be 0.472. The lower and upper 90% confidence limits for the GMR will be given by OBS/1.60 and OBS\*1.60 for AUC0-inf, where OBS is the observed GMR. Thus, for example, if the observed GMR for AUC0-inf was 1.50, then the approximate 90% CI for the GMR would be [0.94 to 2.40].

Similarly, the observed between-participant coefficients of variation were 26.04% (~0.256 standard deviation on the log scale) and 25.25% (~0.249 standard deviation on the log scale) for Cmax from Protocols 002 and 006, respectively. Assuming a sample size of 8 participants per population and observed between-participant SD is 0.256 on the log scale, then the half width of the 90% CI of GMR for MK-6482 Cmax on the log scale will be 0.211. The lower and upper 90% confidence limits for the GMR will be given by OBS/1.23 and OBS\*1.23 for Cmax. Thus, for example, if the observed GMR for Cmax was 1.50, then the approximate 90% CI for the GMR would be [1.22 to 1.85].

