## 2.2.2.3 Clinical Studies

As of a cutoff date of 15-JUN-2021, MK-6482 has been administered as single or multiple doses to a total of 135 healthy participants. In addition, MK-6482 is being evaluated as monotherapy or in combination with other anticancer treatments in participants with solid tumors.

Based on the overall integrated safety summary of MK-6482 monotherapy (N=181) across MK-6482-001 and MK-6482-004 studies, the adverse drug reactions identified for MK-6482 include anemia due to decreased EPO, fatigue, nausea, dyspnea, hypoxia, and dizziness. Most anemia events were  $\leq$ Grade 2. Anemia is an on-target effect of MK-6482 because of the impact of HIF on EPO expression and reduction in EPO and HGB levels with MK-6482 administration. Anemia has been medically managed with erythropoiesis stimulating agent administration and/or blood transfusion as indicated and dose interruption/reduction. Hypoxia is managed by oxygen supplementation as indicated and dose interruption/reduction. Anemia due to decreased EPO and hypoxia should be closely monitored and medically managed as indicated.

Single MK-6482 doses up to 200 mg have been evaluated in 4 completed single-dose Phase 1 studies in healthy participants, and multiple daily doses up to 7 days of 120 mg have been administered to healthy participants in the completed midazolam DDI study (MK-6482-009). MK-6482 was generally well tolerated in these studies. All reported AEs were categorized as either mild or moderate in intensity. In healthy participant studies, there have been no SAEs and no discontinuations due to AEs attributed to MK-6482 treatment. There have been no reports of anemia, hypoxia, or fatigue in the completed healthy participant studies. In addition, no clinically significant reductions in HGB or HCT have occurred in healthy participants in the 4 completed single-dose Phase 1 studies. Mean reductions in HGB and HCT of about 12% from baseline were observed in the completed midazolam DDI study (MK-6482-009) after multiple daily doses of 120 mg, consistent with the anticipated ontarget effect of EPO suppression for MK-6482.

A summary of the MK-6482 clinical development program is contained in the IB supplied by the Sponsor. The IB should be reviewed in conjunction with this study protocol.

MK-6482-020-02 FINAL PROTOCOL

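### Section 9.10 misnames the source of its variability, and its CI widths rest on an unverified common SD and a normal quantile that the planned analysis does not use

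*Combined protocol and SAP*

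**What the plan says.** Section 9.10 (Sample Size and Power Calculations) says that the sample size was not set by any statistical requirement. It then offers precision estimates "based on these sample sizes and the known variability obtained from hepatic PK studies are presented below".

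The variability it reports next is, for AUC0-inf: "The observed between-participant coefficients of variation were 62.44% (~0.574 standard deviation on the log scale) and 56.29% (~0.525 standard deviation on the log scale"; these values are given "for AUC0-inf from food-effect study (Protocol MK-6482-002) and comparative bioavailability study (Protocol MK-6482-006), respectively". For Cmax the values are "26.04% (~0.256 standard deviation on the log scale) and 25.25% (~0.249 standard deviation on the log scale", attributed to the same two protocols.

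One SD per parameter goes into the calculation: "Assuming a sample size of 8 participants per population and observed between-participant SD is 0.574 on the log scale", and likewise "Assuming a sample size of 8 participants per population and observed between-participant SD is 0.256 on the log scale". The results are:

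- AUC0-inf: half-width 0.472, factor 1.60, and a 90% CI of 0.94 to 2.40 for an observed GMR of 1.50.
- Cmax: half-width 0.211, factor 1.23, and a 90% CI of 1.22 to 1.85 for the same GMR.

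Section 9.6.2 (PK Statistical Analysis) specifies a different structure for the interval that will be reported. Its covariance structure "will be used to allow for unequal population variances", with Kenward-Roger denominator degrees of freedom. The t-distribution is named for the group means, and the CI for the difference comes from the same model.

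**The concern.** Two things do not fit together.

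First, 9.10 names one source of variability and uses another. A reader of the opening sentence would take it that variability in hepatically impaired participants is already reflected in the widths. No hepatic study is named and no SD from impaired participants is given.

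Second, the precision calculation is not the planned analysis. It assumes a common SD without saying so and uses a normal quantile. Section 9.6.2 allows the variances to differ and uses a t reference, which matters with 8 participants per group.

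What is at stake is how the expected precision of the GMR is read. These half-widths and example CIs are the only quantitative precision statement in the plan.

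**Working it through.** **Inputs.** From 9.10: n = 8 per group; CVs of 62.44% and 56.29% (AUC0-inf) and 26.04% and 25.25% (Cmax); SDs used, 0.574 and 0.256. From 9.6.2: a two-sided 90% CI, group-specific variances, Kenward-Roger df.

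**1. CV to log SD.** SD = sqrt(ln(1 + CV²)) gives 0.574, 0.525, 0.256 and 0.249. All four match.

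**2. The plan's own widths.** Half-width = 1.645 × SD × sqrt(1/8 + 1/8) = 1.645 × SD × 0.5.

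- AUC0-inf: 1.645 × 0.574 × 0.5 = 0.472; exp(0.472) = 1.60; for GMR 1.50, 0.94 to 2.40.
- Cmax: 1.645 × 0.256 × 0.5 = 0.211; exp(0.211) = 1.23; for GMR 1.50, 1.22 to 1.85.

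The stated figures reproduce. They need both a common SD and the normal quantile.

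**3. Planned type of interval, equal SDs.** With 8 per group and equal variances the df are 14, the most this unequal-variance comparison can have. The quantile is 1.761.

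- AUC0-inf: 1.7613 × 0.574 × 0.5 = 0.505; factor 1.66; for GMR 1.50, 0.90 to 2.49.
- Cmax: 1.7613 × 0.256 × 0.5 = 0.225; factor 1.25; for GMR 1.50, 1.20 to 1.88.

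The log-scale half-width is 1.7613/1.6449 = 1.07 times the stated one, before any question about the SD arises.

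**4. Unequal SDs (assumed range).** The documents give no SD for impaired participants. Let r be the impaired:control SD ratio, with the control SD at the stated value. Then SE = SD × sqrt((1 + r²)/8), and the Satterthwaite df, used here to approximate Kenward-Roger, are 7(1 + r²)²/(1 + r⁴).

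| r (assumed) | df | AUC0-inf half-width, t | AUC0-inf factor, t | AUC0-inf factor, normal | CI for GMR 1.50, t | Cmax factor, t |
|---|---|---|---|---|---|---|
| 0.75 | 13.0 | 0.449 | 1.57 | 1.52 | 0.96 to 2.35 | 1.22 |
| 1.00 | 14.0 | 0.505 | 1.66 | 1.60 | 0.90 to 2.49 | 1.25 |
| 1.25 | 13.4 | 0.574 | 1.78 | 1.71 | 0.84 to 2.66 | 1.29 |
| 1.50 | 12.2 | 0.651 | 1.92 | 1.83 | 0.78 to 2.88 | 1.34 |

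The normal-quantile column isolates the SD effect; the gap between the two factor columns is the quantile effect. If r is below 1, the SD effect runs the other way: at 0.75 the t factor of 1.57 is below the stated 1.60.

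**The case against.** The case for leaving 9.10 alone has several parts.

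- **The widths are labelled as conditional.** Section 9.10 presents them as holding for an assumed variability, and the calculation is an 8-versus-8 comparison of the impaired/normal GMR. This stands. A reader might infer that the widths are not those of an impaired-versus-healthy comparison at all; that goes too far. What is missing is a statement that the assumption is a common SD, and where that SD comes from.
- **The populations of 002 and 006 are not stated.** Section 2.2.2.3 says that single doses up to 200 mg "have been evaluated in 4 completed single-dose Phase 1 studies in healthy participants", without naming those studies. It is therefore tempting, but not documented, to call the figures healthy-versus-healthy.
- **Nothing shows that impaired participants vary more.** A reader might infer it from the Child-Pugh range of 7 to 9, the bilirubin quota or the permitted chronic medication. But the quota is a minimum of five, so all eight could fall in the bilirubin band, and no document gives an exposure difference between bilirubin strata. Section 6.5 requires a stable regimen and restricts inhibitors and inducers of the relevant enzymes. Dual poor metabolizers are excluded from both groups. The direction stays open.
- **The plan took the larger of its two SDs.** This gives some cushion. With 0.525 and the t quantile the AUC0-inf half-width would be 1.7613 × 0.525 × 0.5 = 0.462, factor 1.59. But 9.10 states its widths for 0.574, and for that SD the t interval is wider.
- **No decision depends on the widths.** Section 9.10 says that N met no statistical requirement, Section 4.2 attributes it to FDA guidance, and the final CI will use the observed variances. This stands and limits the importance of the point.

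**Conclusion.** The point holds in a limited form. The attribution to hepatic PK studies is contradicted by the next paragraph of the same section. The stated widths depend on a common SD that is neither declared nor supported by any value for impaired participants.

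For the interval type in 9.6.2 the stated widths are slightly too narrow even if that common SD is right: 0.505 against 0.472 for AUC0-inf, and 0.225 against 0.211 for Cmax. This rests on the t reference applying to the difference as it does to the group means, which follows from the model and df method specified. The figures in step 3 take equal group variances.

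The documents do not support the stronger inference that true precision must be much worse because impaired participants are more variable. Over an assumed SD ratio of 0.75 to 1.5 the AUC0-inf factor runs from 1.57 to 1.92, on both sides of the stated 1.60. Nor do they support reading this as a flaw in the choice of N, which these figures did not set.

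**What to change.** In 9.10:

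1. Replace the reference to hepatic PK studies with the two studies actually used, MK-6482-002 (food effect) and MK-6482-006 (comparative bioavailability). The sponsor should state the population of each.
2. State that one SD is assumed for both groups because no SD for impaired participants is given.
3. Restate the figures with the planned t interval at equal SDs. AUC0-inf: half-width 0.505, factor 1.66, example CI 0.90 to 2.49. Cmax: half-width 0.225, factor 1.25, example CI 1.20 to 1.88.
4. Optionally, add a sensitivity range that runs in both directions and is labelled as an assumption: an impaired:control SD ratio of 0.75 to 1.5 gives AUC0-inf factors of 1.57 to 1.92.

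The cost is a few lines of text and a slightly less favourable stated precision. N, conduct and the analysis model stay as they are.

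### Section 9.10's 90% CI half-widths (0.472 for AUC0-inf, 0.211 for Cmax) use the normal quantile, but Section 9.6.2 plans t-based Kenward-Roger intervals; at 8 per group they should be about 7% larger

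*Combined protocol and SAP*

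**What the plan says.** Section 9.10 says that the sample size "was not chosen to satisfy any a priori statistical requirement" and then describes the precision that 8 per group should give. For AUC0-inf the condition is "Assuming a sample size of 8 participants per population and observed between-participant SD is 0.574 on the log scale", and the result is that "the half width of the 90% CI of GMR for MK-6482 AUC0-inf on the log scale will be 0.472". This leads to limits of the observed GMR divided and multiplied by 1.60, and to an example interval of 0.94 to 2.40 at an observed GMR of 1.50. For Cmax, with SD 0.256, the text says that "the half width of the 90% CI of GMR for MK-6482 Cmax on the log scale will be 0.211", with a factor of 1.23 and an example of 1.22 to 1.85. The section does not name the quantile.

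Section 9.6.2 fits a mixed model to the log-transformed parameters with a separate variance for each population. The intervals for the population least-squares means "will be constructed on the natural log scale and will reference the t-distribution". Kenward and Roger's method "will be used to calculate the denominator degrees of freedom for the fixed effect (DDFM=KR"). The 90% CI for the difference, which gives the GMR interval, is taken from the same model.

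On the source of the variability, the lead-in to Section 9.10 refers to "the known variability obtained from hepatic PK studies are presented below". The CVs that follow are given "for AUC0-inf from food-effect study (Protocol MK-6482-002) and comparative bioavailability study (Protocol MK-6482-006), respectively", and the Cmax CVs come from the same two protocols.

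**The concern.** The precision statement and the analysis plan should describe the same interval. Because N was not set by a power or precision target, these half-widths are the protocol's only quantitative statement of what 8 per group delivers on the primary PK endpoints. A normal multiplier treats the SD as known. The planned model estimates two variances from 8 participants each, and at that size the difference between the normal and t quantiles is visible in the second decimal of the fold-limits. A reader of Section 9.10 would therefore expect a tighter interval than the planned method gives at the stated SD.

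The source wording is a separate, clerical point. It suggests that the SDs reflect variability in hepatic impairment studies, but the section cites none.

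**Working it through.** **Inputs.** From Section 9.10: n = 8 per group; SD of ln AUC0-inf 0.574 (CV 62.44%); SD of ln Cmax 0.256 (CV 26.04%); 90% two-sided interval. The CV conversions agree: √ln(1 + 0.6244²) = 0.574 and √ln(1 + 0.2604²) = 0.256. From Section 9.6.2: separate group variances, DDFM=KR, GMR interval from that model.

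**Standard error of the log difference.** SD × √(1/8 + 1/8) = 0.5 × SD.

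**Reproducing the stated figures** with the normal quantile 1.6449:

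- AUC0-inf: 1.6449 × 0.574 × 0.5 = 0.4721; exp = 1.603
- Cmax: 1.6449 × 0.256 × 0.5 = 0.2105; exp = 1.234

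These are the stated 0.472 / 1.60 and 0.211 / 1.23.

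**Degrees of freedom under the planned model.** Section 9.10 conditions on one observed SD, s, for both groups. The Satterthwaite formula then gives (2s²/8)² ÷ [2 × (s²/8)²/7] = 14. This is the maximum at 8 versus 8; unequal observed variances move it towards 7. The 95th percentile of t with 14 df is 1.7613, and 1.7613 / 1.6449 = 1.071.

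**Figures on the t basis, 14 df:**

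| | Stated half-width | t, 14 df | Stated factor | t, 14 df | Stated CI at GMR 1.50 | t, 14 df |
|---|---|---|---|---|---|---|
| AUC0-inf | 0.472 | 1.7613 × 0.574 × 0.5 = 0.505 | 1.60 | 1.66 | 0.94 to 2.40 | 0.90 to 2.49 |
| Cmax | 0.211 | 1.7613 × 0.256 × 0.5 = 0.225 | 1.23 | 1.25 | 1.22 to 1.85 | 1.20 to 1.88 |

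**Alternative origin.** With t and 16 df at 9 per group the half-widths are 0.4724 and 0.2107, which also match the stated values. A slip in n therefore cannot be excluded, but the text says 8, and the figures do not fit 8 per group with a t-based interval on either explanation.

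**Allowing the sample variances to vary.** A simulation of 400,000 draws used equal true SDs, 8 per group, and Satterthwaite df in place of Kenward-Roger:

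- Mean df: 12.6.
- Median half-width: 0.498 for AUC0-inf (10th to 90th percentile 0.38 to 0.63) and 0.222 for Cmax.
- Share of realised half-widths above the stated value: about 60% for each endpoint.

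**The case against.** The strongest reply is that nothing depends on these numbers. N was not derived from them, no equivalence bound or decision rule uses them, and the reported interval will come from PROC MIXED. That is correct, and it limits the consequence to the planning statement.

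A second reply is that the section offers approximate planning figures based on assumed variability, for which a normal quantile is natural. This holds only in part. The word "approximate" is attached to the example intervals, whereas the half-widths are given to three decimals as what they will be, and the condition is an observed SD, not a known one.

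Third, the gap is small beside the uncertainty in the SD. Section 9.10 uses the larger of its two AUC0-inf SDs. With 0.525 and t on 14 df the half-width is 0.462, below the stated 0.472. That is a fair point about scale, but 0.525 is not what the calculation assumes, and it does not help Cmax: SD 0.249 gives 0.219, still above 0.211.

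Fourth, 7% is conditional on both observed SDs equalling the planning value. In the simulation the medians are about 5% above the stated figures. The protocol also allows a ninth impaired participant, which at equal SDs would give 0.489 and 0.218, about 3.5% above. Both qualifications are right, and in each case the stated figures remain too narrow.

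Finally, the explicit reference to the t-distribution in Section 9.6.2 concerns the group means. For the GMR interval the t basis follows from DDFM=KR and the use of the same model. That inference is sound.

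**Conclusion.** The concern holds. At 8 per group and the SDs that Section 9.10 itself uses, the stated half-widths, fold-limits and example intervals are those of a normal-quantile interval and are too narrow for the analysis in Section 9.6.2. The half-widths should be 0.505 and 0.225, an increase of 7.1% before rounding. This rests on equal observed SDs in the two groups, hence 14 df. With the average variance held at the planning value, unequal observed SDs would widen the gap, to about 15% at the 7 df limit.

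The effect is confined to the precision statement. The AUC0-inf example still includes 1 and the Cmax example still excludes it, and neither N nor the analysis is affected. The wording about hepatic PK studies is inaccurate but has no numerical effect.

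**What to change.** In Section 9.10, state that the figures use the t-distribution with 14 df and equal observed SDs, and replace them as follows:

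- AUC0-inf: half-width 0.505; limits OBS/1.66 and OBS × 1.66; example 0.90 to 2.49.
- Cmax: half-width 0.225; limits OBS/1.25 and OBS × 1.25; example 1.20 to 1.88.

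Add a sentence that the unequal-variance model will usually have slightly fewer degrees of freedom. The simulated average of about 12.6 under equal true SDs can be quoted, but it is optional.

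Reword the lead-in so that it attributes the variability to between-participant data from Protocols MK-6482-002 and MK-6482-006.

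The cost is six numbers, one phrase and a short note. The stated precision becomes slightly less favourable; no participants are added and the analysis is unchanged.
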